2. LAY SUMMARY

Patient-reported outcome measures (PROMs) are questionnaires that measure aspects of somebody's health, like hand function. They can monitor a person's health over time. Our team has made a smartphone app that make these questionnaires shorter. Previous research suggests that unlike the full-length questionnaire, people do not mind using the app every day. This could show us how quickly people recover after different types of hand surgery.

We want to see whether our app could be used to compare patients' experiences of recovery after different types of hand surgery. We will look at operations where we expect to see differences in patients' recovery, and check whether the app is detecting these.

We will recruit patients having different types of treatment for:

- 1) Dupuytren's contracture (when tight fibres cause the finger to bend down towards the palm)
- 2) Fingers that get stuck in a bent position (trigger finger)
- 3) Arthritis at the base of the thumb
- 4) A trapped nerve in the wrist (carpal tunnel syndrome)

Patients will use the app for 3-6 months after surgery. For each condition, we will compare how patients recovered from the different types of treatment.

We also want to know whether the app could be used for remote dynamic/interactive follow up of patients after two common procedures (carpal tunnel decompression and injections to the base of the thumb), instead of having the patient attend a clinic appointment at routine, fixed, time points. We will check whether clinicians could have avoided seeing each patient in clinic, based on the information from the app, or timed the appointment to better meet the patient's needs. To see if people like using the app, we will check how frequently they used it, and interview them about their experience.

3. SYNOPSIS

Study Title	Ecological Momentary Computerised Adaptive Testing to monitor and compare recovery after hand surgery					
Internal ref. no. / short title	EMCAT-2					
Study registration						
Sponsor		RGEA [name]				
Funder	The Oxfordshire Health Ser Surgery of the Hand	vices Research Committee and the	British Society for			
Study Design	Mixed-methods, observation	onal study				
Study Participants	Adults undergoing treatmer criteria)	Adults undergoing treatment for a range of hand conditions (see inclusion criteria)				
Sample Size		Target to meet primary objective: 396 Total required to reach statistical power in all non-essential objectives: 1782				
Planned Study Period	01/06/2024 – 16/12/2026					
Planned Recruitment period	01/06/2024 - 01/06/2026					
	Objectives	Outcome Measures	Timepoint(s)			
Primary	Compare the recovery trajectories of patients undergoing percutaneous needle fasciotomy (PNF) to patients undergoing limited fasciectomy (LF), to test whether EMCAT can detect different recovery trajectories over a 12-week period, with less severe post- treatment symptoms in the PNF group within the first 4 weeks.	Patient Evaluation Measure (PEM), administered via the EMCAT platform	Trajectories will be plotted and compared over a 12-week period.			

Secondary	Compare the recovery trajectories of other groups that are expected to differ (see Section 6)	Patient Evaluation Measure (PEM), administered via the EMCAT platform	Trajectories will be plotted and compared over a 12-week period.
	Assess the usability of the EMCAT platform User Engagement Scale, response rates, response times, semi-structured interviews		12-week follow-up
	Assess the criterion validity of EMCAT against the full-length PEM	PEM (linear format) and EMCAT	Baseline, 6 weeks, 12 weeks
Exploratory	Explore whether information provided by the EMCAT platform could have accurately predicted which patients required a change in management during follow up for open carpal tunnel decompression (CTD)	Accuracy of independent clinician assessment of EMCAT trajectory against the recorded consultation outcome	2 weeks and 12 weeks, or whenever follow- up is timed
	Explore whether information provided by the EMCAT platform could help to time follow- up appointments for TBOA injections to coincide with patient need	Plots comparing follow-up appointment dates to EMCAT trajectories	Over 24 weeks
Intervention(s)	Not applicable	1	
Comparator	Not applicable		

4. ABBREVIATIONS

AWS	Amazon Web Service
CAT	Computerised Adaptive Test
CI	Chief Investigator
CTD	Carpal Tunnel Decompression
EMA	Ecological Momentary Assessment
EMCAT	Ecological Momentary Computerised Adaptive Testing
GCP	Good Clinical Practice
GDPR	General Data Protection Regulation
HRA	Health Research Authority
ICMJE	International Committee of Medical Journal Editors
LF	Limited Fasciectomy
NDORMS	Nuffield Department of Orthopaedics Rheumatology and Musculoskeletal Sciences
NHS	National Health Service
OA	Osteoarthritis
PEM	Patient Evaluation Measure
PI	Principal Investigator
PNF	Percutaneous Needle Fasciotomy
PPI	Patient and Public Involvement
PROM	Patient Reported Outcome Measure
REC	Research Ethics Committee
ТВОА	Thumb-Base Osteoarthritis
UES	User Engagement Scale

5. BACKGROUND AND RATIONALE

Patient-reported outcome measures (PROMs) are questionnaires that can quantify symptom severity from the patient's perspective. In research and clinical practice, PROMs are often administered infrequently. This may fail to capture temporal fluctuations in symptom severity, introduce recall bias (if patients are asked to recall how their symptoms have been over a period of time), and contribute to sampling error (for example, if a patient with an inflammatory disease is measured on a particularly 'good' or 'bad' day). Infrequent PROM administration may also fail to detect differences in early recovery trajectories following interventions.

One solution to this is ecological momentary assessment (EMA)¹. In EMA, patients complete serial PROM assessments in their natural (ecological) surroundings to report on their health state at the time of the assessment (momentarily). While this is appealing for research and clinical care, the usefulness and uptake of EMA is limited by the response burden caused to patients.

Computerised adaptive testing (CAT) describes the use of algorithms to shorten and personalise PROMs². After the response to an item, CAT algorithms estimate the person's score, and select the next most useful remaining item, based on the score estimate. This is repeated with increasing precision until a prespecified stopping rule is met, for example after reaching a measurement precision threshold. By selecting only the most relevant items for an individual, CAT can produce scores that are very similar to full-length PROM scores from a fraction of items in the PROM. Through CAT, we could deliver higher-frequency and lower-burden EMA with better acceptability to respondents, clinicians and trialists. We have termed this concept ecological momentary computerized adaptive testing (EMCAT).

In simulation studies, our team has shown that CAT can deliver precise measurements from a median of 2 items from the 11-item Patient Evaluation Measure (PEM, a PROM used to measure hand function)³. Following this, we built a smartphone application that administers the PEM via EMCAT. We deployed this in a feasibility study involving 40 patients with either thumb base osteoarthritis (TBOA) or recent hand trauma, monitored via EMCAT for 12 weeks. EMCAT significantly reduced the length of the PEM and the time taken to complete it (median 8.8 seconds, vs 1 minute 14 seconds). The median response rate for daily assessments was 93%.

We believe EMCAT could aid the assessment of recovery trajectories in comparative research studies, for example when a new procedure is believed to result in faster recovery times than the current standard of care. This latter point is particularly relevant to the field of hand surgery, where 3 of the top 10 James Lind Alliance research priorities relate to accurate and user-friendly PROM administration, and the assessment of interventions that may improve recovery time, such as arthroplasty for the treatment of TBOA⁴.

There is also potential for EMCAT to be used in clinical practice, as a remote monitoring tool. Daily EMCAT assessments might help to detect early issues in postoperative recovery and facilitate early intervention. It may be appropriate to follow-up patients with reassuring EMCAT trajectories virtually, rather than with expensive and burdensome face-to-face appointments. Interval EMCAT assessments could be employed in the longer term, using the principles and lower burden of EMCAT, to improve PROM completion in late clinical follow-up. These principles could be expanded beyond measuring outcomes in the hand.

In conditions that require repeat treatments to manage a patient's symptoms (for example, steroid injections for TBOA), it may be possible to use EMCAT to time treatments to coincide with peaks in a patient's symptom severity. This could potentially improve health outcomes over time. It may also help to mitigate healthcare inequalities that occur when patients who are unable to attend rigid face-to-face clinic appointments go unassessed.

Clinical Research Protocol Template version 15.0 CONFIDENTIAL © Copyright: The University of Oxford and Oxford University Hospitals NHS Foundation Trust 2019 Page 12 of 33 Here, we propose a cohort study (EMCAT-2) that will assess the potential for EMCAT to detect early between-group differences in recovery trajectory, where conventional PROM administration might not. We will also explore the feasibility of EMCAT-based follow-up, through mixed methodology. The goal of EMCAT-2 is to provide preliminary data to support a range of different research avenues, which will all stem from this single study.

6. OBJECTIVES AND OUTCOME MEASURES

Objectives	Outcome Measures	Timepoint(s) of evaluation of this outcome measure (if applicable)
Primary Objective		
1. Compare the recovery trajectories of patients undergoing percutaneous needle fasciectomy (PNF) to patients undergoing limited fasciectomy (LF), to test whether EMCAT can detect different recovery trajectories over a 12-week period, with less severe post-treatment symptoms in the PNF group within the first 4 weeks.	The PEM, administered via EMCAT.	Trajectories will be plotted and compared over a 12-week period.
Secondary Objectives		
2. Compare the recovery trajectories of other groups that are expected to differ over a 12-week period. Specifically, we will test the following hypotheses, which are based on the researchers' clinical experience:	The PEM, administered via EMCAT.	Trajectories will be plotted and compared over a 12-week period.
 Steroid injection results in less severe post-treatment symptoms than trapeziectomy, within the first 4 weeks 		
 Trapeziometacarpal arthroplasty results in less severe post- treatment symptoms than trapeziectomy, within the first 4 weeks 		
 Minimally invasive (endoscopic or percutaneous) CTD results in less severe post-treatment symptoms than open CTD, within the first 2 weeks 		
 The difference in the recovery of groups undergoing open release vs steroid injection for trigger finger are not clinically significant over the first 2 weeks 		
The objective is to test EMCAT's ability to differentiate between recovery trajectories that are expected to differ, rather than to prove or disprove that differences in recovery trajectory exist. The clinical comparisons are a vehicle for testing the measurement properties of EMCAT. Here, the threshold for clinically significant difference is approximated as half a standard deviation of baseline scores of groups being compared. Statistical significance is taken at the 5% level. By symptom severity, we mean PEM EMCAT scores, where a higher (poorer) score reflects more severe symptoms (a poorer level of hand health).		

	UES scores,	12-week follow-up
3. Assess the usability of the EMCAT platform	response rates, response times, and semi- structured interviews	
4. Assess the criterion validity of EMCAT against the full-length PEM by comparing scores at baseline, 6 weeks, and 12 weeks	Full-length PEM scores and EMCAT PEM scores	Baseline, 6-week and 12-week follow-up
Exploratory Objectives		
5. Explore whether information provided by the EMCAT platform could have accurately predicted which patients required a change in management during open CTD follow up	Accuracy of independent clinician interpretation of EMCAT trajectories against observed patient management	2 weeks and 12 weeks, or whenever follow- up is timed
6. Explore whether information provided by the EMCAT platform could help to time follow-up appointments for TBOA injections to coincide with patient need	Plots comparing follow-up appointment dates to EMCAT trajectories	Over 24 weeks
7. Explore the patient and clinician perceptions of EMCAT-guided follow-up and clinical monitoring	Semi-structured interviews	

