7. STUDY DESIGN

We will perform a mixed-methods cohort study to explore the feasibility of EMCAT for measuring between-group differences in postoperative recovery, its potential to guide follow-up type (face-to-face, telemedicine or patient-initiated) in open carpal tunnel decompression, and its potential to guide follow-up timing after steroid injection for TBOA. The study setting will be NHS hospitals in the England, Scotland and Wales.

Our primary objective is to use EMCAT to compare the recovery trajectories of patients undergoing PNF and LF for Dupuytren's disease. We expect to see a difference in recovery trajectory over a 12-week period, with patients undergoing PNF showing less severe symptoms than those undergoing LF over the first 4 weeks. To meet this objective, we will recruit 396 participants (198 undergoing PNF and 198 undergoing LF), who will be followed up for a 12-week period with daily EMCAT assessments.

To address our secondary objectives, we will simultaneously recruit patients undergoing:

- Steroid injection for TBOA
- Steroid injection for trigger finger
- Trapeziectomy for TBOA
- Arthroplasty for TBOA
- Surgical release of trigger finger
- Open CTD
- Minimally invasive (endoscopic or percutaneous) CTD

We will recruit as many participants as we can in these groups, within the limits of the study timing and funding, and up to a maximum of 198 per group. We will use all collected EMCAT data to test the following hypotheses:

- Steroid injection results in less severe post-treatment symptoms than trapeziectomy, within the first 4 weeks
- Trapeziometacarpal arthroplasty results in less severe post-treatment symptoms than trapeziectomy, within the first 4 weeks
- Minimally invasive (endoscopic or percutaneous) CTD results in less severe post-treatment symptoms than open CTD, within the first 2 weeks
- The difference in the recovery of groups undergoing open release vs steroid injection for trigger finger are not clinically significant over the first 2 weeks

The objective is to test EMCAT's ability to differentiate between recovery trajectories that are expected to differ, rather than to prove or disprove that differences in recovery trajectory exist. The clinical comparisons are a vehicle for testing the measurement properties of EMCAT.

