11.4 Description of the Statistical Methods

The hypotheses outlined in the primary and secondary objectives will be tested with mixed-effects linear modelling. These models will comprise: EMCAT score (continuous dependent variable on a logit scale, derived from a graded response model); participant number (random intercept); age, sex, and baseline score (fixed effects); and an interaction term between time (number of days following the intervention) and treatment allocation. Marginal means will be derived from these models and between-group differences calculated at daily timepoints after Tukey adjustment for multiplicity. This will be performed with the *emmeans* R package, or equivalent software. For each comparison, marginal means will be plotted, and differences compared to a minimal important difference (MID) estimate of half a standard deviation of baseline scores. Clinically and statistically significant (at the 5% level) differences will be compared to those predicted (see section 6).

EMCAT completion rates (number of completed response sets divided by number of invitations), response times, and UES scores will be analysed through descriptive statistics. The UES was originally intended to measure 6 user engagement constructs, but subsequent studies have suggested that it follows a 4-factor structure. Items of the UES will be grouped into the 4 subscales described by O'Brein et al, to measure: focused attention, aesthetic appeal, perceived usability and reward⁵.

The criterion validity of the EMCAT scores against the full-length PEM scores will be assessed by comparing pairs of EMCAT scores and full-length PEM scores that were obtained from the same participant on the same day. Comparison will be made by calculating Pearson's correlation coefficient, mean absolute error, root mean squared error and the Bland-Altman method⁶.

In Stream 2, three independent clinicians will review EMCAT trajectories (presented as time series plots) and follow-up appointment dates for participants that underwent open CTD. They will be asked to predict whether a change in management was required at the follow-up appointment. We will calculate inter-rater reliability of these assessments (Fleiss' kappa) and, for each clinician, the accuracy, sensitivity, specificity, positive predictive value and negative predictive value of their predictions against the reference standard (whether or not the patient received a change in management).

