11.5 Sample Size Determination

Our primary objective is to use EMCAT to compare the recovery trajectories of patients undergoing PNF and LF for Dupuytren's disease. To have a 90% chance of detecting a moderate effect size of 0.35 between groups on a z-score scale (with a standard deviation of 1), at the 5% significance level, 344 patients are required for each comparison (172 per group). Assuming a 15% attrition, this leaves a target sample size of 396 for the primary objective (198 per group).

Objective 2 (see section 6) sets out 4 more comparisons, involving 7 other groups of patients:

- Steroid injection for TBOA
- Steroid injection for trigger finger
- Trapeziectomy for TBOA
- Arthroplasty for TBOA
- Surgical release of trigger finger
- Open carpal tunnel decompression
- Minimally invasive (endoscopic or percutaneous) carpal tunnel decompression

At 198 participants per group, and 9 groups total, a further 1386 participants (1782 total) would be required to reach statistical significance in all of our secondary (non-essential) objectives. We will recruit as many participants as we can in these groups, within the limits of the study timing and funding, and up to a maximum of 198 per group.

In summary, our recruitment target is 396 (172 participants undergoing LF and 172 participants undergoing PNF), but we will recruit up to a maximum of 1782 participants (198 in each of the groups described above).

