11.9 The Level of Statistical Significance

Clinical Research Protocol Template version 15.0

CONFIDENTIAL

© Copyright: The University of Oxford and Oxford University Hospitals NHS Foundation Trust 2019 Page 24 of 33 Statistical significance will be defined at the 5% level.

11.10 Procedure for Accounting for Missing, Unused, and Spurious Data.

Data which are clearly spurious will be excluded. Missing data will be described. For each variable, the association of missingness and the values of other variables will be analysed through descriptive statistics. All available data will be used to fit the models used for the primary analysis. We will not impute missing data and do not plan to undertaken any sensitivity analyses.

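### The trigger-finger hypothesis of no clinically significant difference is an equivalence claim, but section 11.4 judges it by difference tests with no interval criterion and no inconclusive outcome

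*Protocol*

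**What the plan says.** - **Hypothesis.** Sections 6 and 7 list, among the secondary hypotheses to be tested, that differences for "open release vs steroid injection for trigger finger are not clinically significant over the first 2 weeks".
- **Threshold.** Section 6 adds: "Here, the threshold for clinically significant difference is approximated as half a standard deviation of baseline scores of groups being compared".
- **Analysis.** Section 11.4 puts the primary and secondary hypotheses through one mixed-model procedure, with "between-group differences calculated at daily timepoints after Tukey adjustment for multiplicity". Marginal means are plotted and differences set against the half-SD minimal important difference (MID). The concluding step is: "Clinically and statistically significant (at the 5% level) differences will be compared to those predicted".
- **Level.** Section 11.9: "Statistical significance will be defined at the 5% level".
- **Group sizes.** For the secondary groups, section 7 says "We will recruit as many participants as we can in these groups, within the limits of the study timing and funding", up to 198 per group. No minimum is given.
- **Sample size.** The only calculation in section 11.5 is for detecting a 0.35 SD difference. Section 11.5 says that 1386 further participants "would be required to reach statistical significance in all of our secondary (non-essential) objectives".
- **No other plan.** Section 11.3 states that no separate SAP is in use, so section 11.4 is the full analysis rule.

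**The concern.** A claim that a difference lies below a stated margin is supported only when the data rule out differences above that margin. Failing to find a significant difference does not do this, because a small or noisy sample also fails to find one. Section 11.4 has no step that separates a difference shown to be small from one that is simply not established.

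This matters for the study's purpose. The protocol describes the clinical comparisons as a means of testing EMCAT's measurement properties, and this is the only hypothesis that predicts no important difference. It is thus the one check that EMCAT does not signal a difference where none is expected. An insensitive instrument or a small sample could pass it under the stated rule.

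**Working it through.** **Inputs from the protocol.** MID 0.5 baseline SD (section 6). Level 5% (section 11.9; two-sided reproduces the stated sample size). SD 1, effect 0.35, power 90%, attrition 15%, cap 198 per group (section 11.5).

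**Assumptions, not in the protocol.** Group sizes below the cap; true differences of 0.5 and 0.75 SD; between-day correlation of 0.6 to 0.8. Residual SD is 1, as in section 11.5, with 0.87 tried as a range because the model adjusts for baseline score.

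**1. The plan's own figure.** n = 2 × ((1.960 + 1.282)/0.35)² ≈ 171.6, so 172 per group and 344 in total. 172 × 1.15 = 197.8, so 198. 7 × 198 = 1386 and 9 × 198 = 1782. All reproduce. The calculation concerns detecting a difference; equivalence power is not addressed.

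**2. The stated rule on one day.** SE = √(2/n). A difference is flagged only if the estimate is at least 0.5 in size and also significant, so the cut-off is c = max(0.5, 1.96 × SE). The chance of no flag at true difference d is Φ((c − d)/SE) − Φ((−c − d)/SE).

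Example, n = 20, d = 0.75: SE = 0.316, c = 0.620, (0.620 − 0.75)/0.316 = −0.41, Φ = 0.34.

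In the table, a range runs from the normal to the t critical value.

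| n per group | d = 0.75: no flag, joint rule | d = 0.75: point estimate below MID | d = 0.5: no flag, joint rule |
|---|---|---|---|
| 10 | 61–66% | 28% | 80–84% |
| 20 | 34–36% | 21% | 65–67% |
| 30 | 17–18% | 17% | 51–53% |
| 50 | 11% | 11% | 50% |
| 198 | 0.6% | 0.6% | 50% |

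The two rules merge near n = 2 × (1.96/0.5)² ≈ 31, because from there any estimate of 0.5 or more is also significant. With residual SD 0.87 and d = 0.75, the joint rule gives 57% at 10 per group and 24% at 20 (t critical values).

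**3. Fourteen days instead of one (simulation, d = 0.75 on every day).**
- If any one unadjusted daily test can refute the prediction, it survives in 23–36% of studies at 10 per group and 5–12% at 20.
- If the adjustment spans the 14 days (Bonferroni as a stand-in), it survives in 77–84% at 10 and 34–49% at 20.
- A Tukey adjustment between two groups within one day changes nothing. The protocol does not say which family of tests is meant.

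**4. An equivalence rule.** Require the 90% CI to lie within ±0.5 SD. False confirmation at a true 0.5 SD is then at most 5% at every group size. Power at a true difference of 0 is 2Φ(0.5/SE − 1.645) − 1:
- 168 analysed per group (198 × 0.85): SE = 0.109, power 99.7%
- 100 per group: SE = 0.141, power 94%
- 50 per group: SE = 0.200, power 61%

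For 90% power, n = 2 × ((1.645 + 1.645)/0.5)² ≈ 86.6, so 87 per group, or 103 after dividing by 0.85 for attrition. If the true difference is 0.2 SD, 191 per group are needed before attrition. At 20 or fewer per group with SD 1 the rule cannot succeed, so the result is inconclusive.

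**The case against.** **The point estimate may be what decides.** Section 11.4 also sets differences against the MID, and section 6 defines clinical significance by size alone. If only the estimate is judged, a small sample does not confirm by default: at 10 per group and a true 0.75 SD, about 28% fall below the MID. This stands as a possible reading. It still ignores uncertainty, and the concluding step in section 11.4 pairs clinical with statistical significance.

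**The effect of sample size is limited.** A reader might infer that less data always makes the prediction easier to confirm, or that the comparison gives no evidence at all. The figures do not support that. Above about 30–50 per group the joint rule behaves like the point estimate, and a true 0.75 SD is missed in only 0.6% of studies at 198. The 50% at exactly 0.5 SD is what any point-estimate rule gives when the truth sits on the threshold.

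**The single-day figures are conditional.** They overstate the problem if any unadjusted day can refute the prediction. This stands.

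**Section 11.5 does not promise significance.** A reader might take its wording as an assurance that every secondary comparison will be significant, and object that 90% power per comparison cannot deliver that. The wording states a requirement, and the synopsis describes the same total of 1782 in terms of statistical power. What remains is loose wording: significance is not the aim of the trigger-finger hypothesis.

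**The objective is secondary.** The protocol calls these objectives non-essential and the study's data preliminary. This bears on priority, not on whether the rule fits the hypothesis.

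**Conclusion.** The point holds. The hypothesis is one of equivalence with a stated margin, and the plan has neither an interval criterion nor an inconclusive outcome for it. Under the joint rule, a true difference of 0.75 SD would be read as not clinically significant in roughly a third of studies at 20 per group and about three in five or more at 10. By 50 per group this is 11%. These figures assume a single day, SD 1 and group sizes that the protocol does not fix; step 3 shows how far the daily rule moves them.

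The planned maximum of 198 per group is ample for an equivalence test when the groups are truly equal, so the fault lies in the decision rule and not in the cap. The correction is recommended for a secondary objective. The primary comparison of needle fasciotomy with limited fasciectomy is unaffected.

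**What to change.** **Section 11.4.** For trigger finger, use the 90% CI for the model-based difference averaged over days 1–14, and keep plotting the daily differences:
- conclude not clinically different only if the CI lies within ±0.5 baseline SD;
- conclude clinically different only if the CI lies wholly outside that margin;
- otherwise report the result as inconclusive.

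**Section 11.5.** Replace the statement about reaching statistical significance in all secondary objectives with one giving 90% power for each superiority comparison at 0.35 SD. State the equivalence power separately (true difference 0, SD 1): about 99.7% at 168 analysed per group, 94% at 100 and 61% at 50.

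**Cost.** A few sentences and no extra participants. Averaging over the two weeks is a choice that the sponsor should confirm, since the protocol compares groups day by day. With few participants the trigger-finger result will be inconclusive.
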